6.6.1.3. Sensitivity analysis

The same analysis performed on the primary endpoints will be conducted on the PPS as sensitivity analysis.

Additionally, a second sensitivity analysis performed on the FAS will be conducted using the following specifications:

Sensitivity Estimands for the primary Endpoint 1 (E1)

1. Treatment: 12 weeks administration of NAC-GED-0507 gel ■% or vehicle gel.
2. Target population: Male and female patients aged ≥ 9 and <50 years affected by facial acne vulgaris. Full Analysis Set.
3. Variable: relative change from baseline in total ■■■■■ (inflammatory plus non-inflammatory) at V5/Wk12 on the face.
4. Intercurrent events (ICEs) and strategies to handle them:
 - Treatment discontinuation
 - Study withdrawal
 - Use of prohibited medications listed in section 5.4.7

A treatment policy strategy will be applied where all observed values will be used regardless of the occurrence of the ICEs. Missing data due to any reason will be handled by using a multiple imputation approach with a missing-at-random (MAR) assumption

5. Population-level summary: the difference in the relative change from baseline to V5/Wk12 in total ■■■■■ between the two treatment groups will be assessed by an independent t-test (or a Wilcoxon test if the Normality is violated).

Sensitivity Estimands for the primary Endpoint 2 (E2)

1. Treatment: 12 weeks administration of NAC-GED-0507 gel ■% or vehicle gel.
2. Target population: Male and female patients aged ≥ 9 and <50 years affected by facial acne vulgaris. Full Analysis Set.
3. Variable: proportion of patients with an IGA success at V5/Wk12.
4. Intercurrent events (ICEs) and strategies to handle them:
 - Treatment discontinuation
 - Study withdrawal
 - Use of prohibited medications listed in section 5.4.7

A treatment policy strategy will be applied where all observed values will be used regardless of the occurrence of the ICEs. Missing data due to any reason will be handled by using a multiple imputation approach with a missing-at-random (MAR) assumption

5. Population-level summary: the difference in terms of the proportion of patients with an IGA success at V5/Wk12 between the two treatment arms will be assessed with an independent Chi-Square test (or Fisher exact test if the successes in one of the two treatment groups is lower than 5).

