6.2. Analysis sets and type of analysis

Screened Analysis Set (SCR)

This analysis set includes all patients who signed the informed consent form and received a screening number, regardless of whether they completed all the screening procedures.

Enrolled Set (ENR)

All patients included in the study, excluding screening failure.

Randomized Set (RND)

All enrolled patients who are randomized to a treatment arm.

Full Analysis Set (FAS)

The Full Analysis Set (FAS) includes all randomized patients who receive at least one dose of the study medication and have at least one valid post-baseline efficacy assessment for both primary endpoints.

The analyses on FAS will be performed with the Intention-To-Treat (ITT) principle.

Per-Protocol Set (PPS)

The Per-Protocol Set (PPS) comprises all patients included in the FAS who complete the study without major protocol deviations. Major protocol deviation will be identified in the SAP and/or during a blind medical review.

The analysis of efficacy will be conducted on the FAS and PPS sets, with the FAS considered as the primary set for statistical analysis, based on treatment as randomized.

Safety Set (SS)

The Safety Set (SS) includes all patients who received at least one dose of study treatment. Safety analyses will be performed on the Safety Set based on treatment as received.

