6.5. Rationale for the sample size

The sample size is based on the two co-primary endpoints: relative change from baseline in total lesion count on the face (inflammatory plus non-inflammatory) and IGA success at V5/Wk12 to reach a power of 90% at a level of 0.05, since this are considered the most relevant clinical endpoints.

The formal calculation of sample size is based on the paper from T. Sozu et al. Sample size for co-primary continuous and binary endpoint (2012), assuming the normality of the relative change from baseline distribution and making the following assumptions:

- an error I type of ■%
- a statistical power of ■%
- a relative change from baseline in total lesion count on the face at V5/Wk12 in the IMP 2-V arm (placebo arm) of ■% (data retrieved from the Study NAC-GED-0507-ACN-01-18)
- a Standard Deviation (SD) of the difference between treatment arms of ■% (data retrieved from the Study NAC-GED-0507-ACN-01-18).
- a rate of IGA success on the face at V5/Wk12 in the IMP 2-V arm (placebo arm) of ■% (data retrieved from the Study NAC-GED-0507-ACN-01-18)
- a difference between the two treatment arms in terms of the relative change from baseline in total lesion count on the face (inflammatory plus non-inflammatory) at V5/Wk12 equal to or greater than ■% and a difference in IGA successes equal or greater than ■% (data retrieved from the Study NAC-GED-0507-ACN-01-18).

A sample size of 366 evaluable patients (183 in each treatment arm), will be adequate to find a significant difference between the two treatment arms in terms of the relative change from baseline in total lesion count on the face (inflammatory plus non-inflammatory) at V5/Wk12 and in IGA successes.

Considering a drop-out rate close to ■% of non-evaluable patients for any reason, a total of 400 patients will have to be enrolled in the study (sample allocation ratio 1:1).

A second pivotal Phase 3 study (NAC-GED-0507-ACN-01-23-B) with an identical study design to the present study is planned to be performed with an equivalent sample size of 400 patients in total.

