8.3. Discontinuation of trial treatment or trial participation for individual patients

8.3.1 Premature discontinuation of trial treatment

The trial patient can have his/her trial treatment terminated prematurely at any time, without having to give reasons.

Patients will be withdrawn from the treatment if their safety or well-being is at risk. Discontinuation will be made at the discretion of the investigator/Sponsor/DSMB or at the patient's request.

The investigator should contact the Sponsor to discuss the withdrawal of a patient who fulfils the discontinuation criteria, prior to discontinuing a patient from the study, unless in those circumstances where the investigator considers that the patient is at immediate clinical risk.

A patient must be discontinued under the following circumstances:

- Withdrawal of consent
- IMP permanent discontinuation for any reason in one or both treated areas
- Pregnancy
- An AE, including intercurrent illness for which the patient desires to discontinue treatment or the investigator determines that it is in the best interest of the patient to be discontinued
- In case of unexpected laboratory out-of-range values in the blood samples collected at screening, which in the Investigator's opinion may pose the patient at increased risk during participation to the clinical trial the patient will be contacted to discontinue the treatment and will be withdrawn from the study.
- Serious concomitant symptoms (e.g., extensive blisters or erosions) in the facial area as well as a local or generalized allergic reaction to the IMP or procedures
- Lost to follow-up.

A patient may be required to discontinue from the trial at any time for the following reasons:

- The patient's treated and not treated acne worsens and requires alternative or supplemental medication during the trial.
- Occurrence of another dermatosis requiring treatment that interferes with the inclusion criteria
- Subsequent disclosure that the inclusion and exclusion criteria were not fulfilled when the patient was enrolled in the trial if the safety and well-being of the patient might be influenced
- At the discretion of the investigator
- Non-compliant use of IMP or protocol requirements
- Treatment code is broken.

In the case trial treatment of a patient has been stopped prematurely, ETV procedures should be conducted as far as possible. The DSMB will be informed accordingly, and all the relevant information provided.

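### The only full-analysis-set sensitivity analysis is labelled treatment policy, but its MAR imputation estimates roughly the effect had gel stoppers continued; neither sensitivity analysis in the protocol tests stoppers losing benefit

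*Protocol*

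**What the plan says.** Protocol section 6.6.1.3 names two sensitivity analyses for the co-primary endpoints, E1 (relative change in facial total lesion count at Week 12) and E2 (IGA success at Week 12).

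- **Per-protocol set (PPS).** "The same analysis performed on the primary endpoints will be conducted on the PPS as sensitivity analysis". Under section 6.2 the PPS "comprises all patients included in the FAS who complete the study without major protocol deviations".
- **FAS.** The intercurrent events listed are treatment discontinuation, study withdrawal and prohibited medication. The strategy is treatment policy, with observed values used whatever the event. For missing values, in the same words for E1 and E2: "Missing data due to any reason will be handled by using a multiple imputation approach with a missing-at-random (MAR) assumption".

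The primary analysis (6.6.1.1 and 6.7) carries the last observation forward.

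Two other sections decide which Week-12 values will exist. Section 8.3.1 lists, among the circumstances in which a patient must be discontinued, "IMP permanent discontinuation for any reason in one or both treated areas", and asks for early termination visit (ETV) procedures as far as possible. Section 5.4.7 discontinues patients who need substitutive acne treatment. The ETV in section 5.5.1 ends the trial for that patient.

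**The concern.** A treatment-policy effect includes what happens after a patient stops gel. Estimating it needs either outcomes observed after stopping or an imputation that reflects having stopped. Under the discontinuation rules the first is almost absent, and 6.6.1.3 does not provide the second: one MAR rule covers all reasons for missingness, with nothing separate for stoppers. The imputation model learns from patients who kept applying gel and predicts what the stopper would have shown by continuing.

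Two things are at stake. The estimate would be reported under the wrong estimand label, and it is too favourable for that label whenever benefit fades after stopping. A reader who sees the FAS and PPS sensitivity analyses agree may also take that as robustness to dropout, although neither asks what happens if active-arm dropouts lose their benefit.

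**Working it through.** **The plan's own figure.** Section 6.5 gives 366 evaluable patients (183 per arm) and 400 enrolled. The planning effects, SD, vehicle rate and drop-out rate are redacted, so 366 can be neither reproduced nor faulted. The arithmetic 1 - 366/400 = 8.5% is the allowance for patients outside the evaluable set. The Synopsis and section 5.1 define 366 as the number in the FAS, so 8.5% is not the share of FAS patients missing Week 12. That share is not given; 5% to 20% is assumed below.

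**Inputs from the protocol** (Phase 2b age subgroups; Synopsis, justification of dose, and section 2):

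- E1: 59.0 - 33.4 = 25.6 points (18 years or younger); 54.6 - 34.6 = 20.0 points (over 18).
- E2: 41.4 - 20.9 = 20.5 points (18 years or younger); 50.8 - 28.8 = 22.0 points (over 18).

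These stand in for the on-treatment difference D.

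**Formula.** Let a share d of active FAS patients stop and become vehicle-like by Week 12, with the vehicle arm unchanged.

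- Treatment-policy difference = (1 - d) x D + d x 0 = (1 - d) x D
- MAR estimate, roughly D
- Overstatement = D - (1 - d) x D = d x D; relative overstatement = d/(1 - d)

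| d | E1, D = 20.0 to 25.6 | E2, D = 20.5 to 22.0 | Relative |
|---|---|---|---|
| 5% | 1.0 to 1.3 points | 1.0 to 1.1 points | 5% |
| 10% | 2.0 to 2.6 points | 2.1 to 2.2 points | 11% |
| 20% | 4.0 to 5.1 points | 4.1 to 4.4 points | 25% |

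**Does MAR return about D for dropouts?** This was simulated for E1 with 200,000 patients per arm. Assumed means at Weeks 4, 8 and 12 were -25, -42, -56 (active) and -15, -26, -34 (vehicle), with SDs 28, 32, 35. Dropout came after Week 4, was likelier in poor Week-4 responders, and left about 9% missing. Imputation was by arm, conditional on Week 4.

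| Week-12 mean | Active | Vehicle | Contrast |
|---|---|---|---|
| Completers, observed | -57.2 | -35.3 | 21.9 |
| Dropouts, MAR | -43.6 | -21.6 | 22.0 |
| Dropouts, LOCF | -5.1 | 4.8 | about 10 |

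MAR places the dropouts at a worse level than completers but keeps the whole between-arm contrast. LOCF keeps less than half of it. In this setting the sensitivity analysis departs from the primary in the favourable direction.

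**Consequence for significance.** E2 power was computed at 183 per arm, two-sided 0.05, treating the data as complete (so without loss of precision from imputation), with 10% of active patients set to the vehicle rate:

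- 41.4% against 20.9%: 99.0% under MAR, 97.3% with vehicle-rate imputation.
- 40% against 25% (assumed; close to the smallest difference detectable with 90% power, about 15 to 16 points): 86.8% and 79.5%.

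**The case against.** The case on the other side is substantial.

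- **The co-primary decision rests on LOCF, not on MAR or the PPS.** This stands. A reader might infer that all planned analyses lean the same way and that the trial's verdict depends on giving stoppers the on-gel benefit. The documents do not support that: LOCF makes a different assumption and in the simulation credits dropouts with much less. But LOCF freezes the last value, often one measured on gel, so it does not test loss of benefit after stopping either.
- **The imputation model is not specified.** It may use Week 4, Week 8 or ETV values, so a patient who left because acne worsened would carry poor values forward. This stands. It rules out reading the plan as giving stoppers the full on-gel level; the claim concerns the between-arm contrast only.
- **The SAP is not shown.** It may add a missing-not-at-random analysis, so a reader cannot conclude that the co-primary results are never stress-tested. What can be judged is that the protocol itself fixes one MAR rule for all reasons under a treatment-policy label. That is a stated rule, not detail left open.
- **Some values after an intercurrent event may be observed.** For worsening acne that needs other medication, 8.3.1 says discontinuation may be required, whereas 5.4.7 says the patient will be discontinued. These passages must be reconciled. The exception concerns prohibited medication; permanent stopping of gel remains a mandatory discontinuation.
- **The size rests on assumptions.** Every d is assumed, and so is a full return to vehicle-like outcomes by Week 12; partial loss gives a smaller overstatement. Taking d = 8.5% from the 400-to-366 allowance would be wrong, because those 34 patients lie outside the FAS. A borderline p-value crossing 0.05 could be constructed, but only from invented rates and with imputation variance left out.

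**Conclusion.** The point holds in a limited form. The FAS sensitivity analysis in 6.6.1.3 is labelled treatment policy but, given the discontinuation rules, estimates approximately the effect had patients continued treatment. Of the two sensitivity analyses the protocol states, this one assumes the on-treatment contrast for stoppers and the PPS analysis removes them, so neither tests active-arm dropouts losing benefit.

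The overstatement relative to the treatment-policy difference is about d x D, or 5% to 25% in relative terms for d between 5% and 20%. This assumes vehicle-like outcomes after stopping, Phase 2b differences as D, and imputation that preserves treatment arm. It is an error in the sensitivity estimate, not in the primary LOCF result. At Phase 2b-sized effects significance would probably survive; the gap matters more near the detectable difference. The change should be made, but the point does not invalidate the primary analysis.

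**What to change.** In section 6.6.1.3, for both E1 and E2 on the FAS:

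1. Add a reference-based multiple imputation (copy-reference or jump-to-reference, named in advance) for Week-12 values missing after stopping active gel, drawing on the vehicle arm. Keep other missing values under MAR.
2. Add a delta-adjusted tipping-point analysis showing how much worse active-arm dropouts would have to be before significance is lost.
3. Relabel the existing MAR analysis as estimating the effect had patients continued treatment.

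The cost is protocol and SAP wording and extra programming, with no new patients, visits or data. The downside is one slightly less favourable estimate per co-primary endpoint. The change should be fixed before unblinding.

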6.6.2. Safety analyses

The analysis of safety will be conducted on the Safety Set.

Adverse events (AEs) will be coded by System Organ Class (SOC) and Preferred Term (PT), using the Medical Dictionary for Regulatory Activities (MedDRA).

Treatment-emergent adverse events (TEAEs), i.e. AEs with an onset on or after the time of the first IMP application, will be analyzed. TEAEs will be summarized by primary system organ class (SOC), preferred term (PT), severity and relationship to IMP.

All local tolerability signs and symptoms (both objective and subjective) will be listed and summarized at each visit by treatment and severity using frequency tables.

The overall application site irritation requested at the end of the study treatment will be listed and summarized using frequency tables by treatment group.

Vital signs will be listed and presented descriptively by visit, including changes from baseline.

Regarding laboratory assessments, the overall investigator's interpretation (as normal [N], abnormal but not clinically significant [NCS] or abnormal and clinically significant [CS]) will be listed and summarized by treatment group using shift tables from Visit 1 to Visit 5/Wk12.

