the study, as well as the number and types of events (i.e. AEs, TEAEs, ADRs, Serious Adverse Events (SAEs)) of events will be summarized according to SOC and PT of MedDRA dictionary.

A patient with multiple AEs within a SOC will only be counted once towards the total of the SOC.

Descriptive statistics will be computed for all other safety endpoints (i.e., vital signs, physical examination, laboratory test, local tolerability-Application site signs/symptoms, overall application site irritation) at applicable time points, as well as changes from baseline by treatment arm.

Patient data listings will be provided as appropriate.

The analysis of baseline and demographics' characteristics will be performed on the RND population. The primary and secondary analyses will be performed on the FAS having the PP as supportive for the primary analysis. The safety analyses will be performed on the SAF.

More details on the statistical analyses will be provided in the Statistical Analysis Plan (SAP).

Date of issue

24JAN2025 (UK)

Signatures of Sponsor

Title A phase III study to assess efficacy and safety of N-Acetyl-GED-0507-34-LEVO gel █%, applied once daily for 12 weeks in patients with acne vulgaris (GEDACNE-1)

Protocol no: NAC-GED-0507-ACN-01-23-A

Protocol version: Final V2.0 (UK only)

Protocol date: 24JAN2025

Document History:

Version	Date	Description of change	Reason for change
1.1	17MAY2024	Original Version	NA
1.2	13AUG2024 (UK ONLY)	Harmonized the information in par. 10.3 with the Patient Information Sheet, in respect of information on treatment choices available to participants, and who they should contact in the circumstances they experience worsening acne. Added in paragraph 5.5.1 that the study visits for school age children should be undertaken outside of school hours. Minor improvements in Appendix C. Minor typos corrections.	MHRA RFI
2.0	24JAN2025 (UK ONLY)	Text added/modified to make processes and procedures more clear. Minor typos corrections.	Need to align the UK version with the one applied in the EU countries

This clinical trial protocol was subject to critical review and has been approved by the Sponsor. The information it contains is consistent with:

- the current risk-benefit evaluation of the investigational product

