- Collection of IMP and diary and assessment of patient compliance by diary check, and counting of tubes
- Schedule next visit.

Follow-up

Visit 6 (Wk14) End of trial Day99 (+ 2days) or ETV in case of withdrawal after EoT – Telephone contact

- Check concomitant medications/therapies and AEs
- End of trial.

If clinically significant out of range or clinically significant values are found at V5, patient will be asked to return at site to perform additional laboratory examinations of the significant out of range values.

This visit will be performed only for patients who are not included in the long-term study.

UNSCHEDULED VISITS (Early termination visit [ETV])

Any time the trial is permanently discontinued for any reason during the treatment phase, an Early Termination visit should be performed:

- Check concomitant medications/therapies and AEs
- Physical examination and measurements of vital signs (blood pressure and heart rate [pulse])
- Collection of samples for determination of laboratory parameters:
 - Standard safety laboratory examinations
 - Blood pregnancy test in childbearing potential women (see **Appendix C** for definition of WOCBP)
- Clinical assessments (lesion count [inflammatory and non-inflammatory lesions] and IGA/PGA). PGA will be evaluated only if the trunk is treated
- [REDACTED]
- [REDACTED] (not mandatory, following specific consent)

- Dermatology Life Quality Index (DLQI) / Children's Dermatology Life Quality Index (C-DLQI for patients from 9 to 16 years old), completed by the patient (prior to any Investigator assessments to not impact the patient's answers to the quality of life questionnaire)
- Evaluation of local tolerability signs/symptoms. The patient will be questioned if he/she experienced any of these subjective symptoms within the last 24 hours prior to visit
- Patient's assessment of overall application site irritation
- Collection of IMP and diary and assessment of patient compliance by diary check, and counting of tubes
- End of trial.

In case the discontinuation is during the Follow-up phase, the Visit 6 (Wk14) End of trial (± 2 days) – Telephone contact procedures will be performed.

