5.5.2.6. Local tolerability assessment

Local safety and tolerability will be evaluated on the basis of the following signs and symptoms:

Objective symptoms

- application site non-lesional erythema
- application site exfoliation
- application site dryness
- overall application site irritation.

Subjective symptoms

- stinging
- burning
- itching.

For all the site visits, objective symptoms (signs of erythema, exfoliation, dryness) will be assessed and scored by the Investigator and the patient will be questioned if he/she experienced any of the subjective symptoms (stinging, burning, itching) within the last 24 hours prior to visit.

During telephone contacts (patients aged 9 to < 12 only), patient will be questioned if he/she experienced any of the above sign/ symptoms within the last 24 hours prior to visit.

For each sign/symptom, a severity score will be assigned using a 4-point scale from 0 = none to 3 = severe (**Tables 5-7 and 9-11**).

Moreover, at baseline, the presence or absence of any of these signs/symptoms in the past 14 days will be collected.

The overall application site irritation will be assessed at baseline (only presence /absence assessment) and the end of study treatment (V5).

At V5, the overall application site irritation will be assigned using a 4-point scale from 0 = excellent to 3 = poor (see **Table 8**).

Only sign/symptom occurring after the first application of study medication that requires additional therapy or discontinuation of treatment or judged clinically significant by the Investigator, will be documented as a TEAE.

Table 5: Scoring of application site non-lesional erythema

Severity	Score	Description
None	0	No erythema
Mild	1	Light pinkness present
Moderate	2	Definite redness, easily recognized
Severe	3	Intense redness

Table 6: Scoring of application site exfoliation

Severity	Score	Description
None	0	No scaling
Mild	1	Barely perceptible shedding, noticeable only on light scratching or rubbing
Moderate	2	Obvious but not profuse shedding
Severe	3	Heavy scale production

Table 7: Scoring of application site dryness

Severity	Score	Description
None	0	No dryness
Mild	1	Slight barely perceptible fine superficial scale
Moderate	2	Clearly perceptible fine scale giving skin a powdery appearance
Severe	3	Marked roughness, cracked skin with fissures

Table 8: Scoring of overall application site irritation

Grades	Score	Description
Excellent	0	No signs of irritation during the study

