6.4. Safety and tolerability endpoints

1. Incidence of all Adverse Events (AEs), Treatment-Emergent Adverse Events (TEAEs), Adverse Drug Reactions (ADRs), Serious Adverse Events (SAEs) throughout the study with special attention to local TEAEs concerning the treated facial area (local dermal safety), and systemic TEAEs
2. Frequency of discontinuation of treatment due to TEAEs
3. Changes from baseline of vital signs during the study
4. Physical examination during the study
5. Changes from baseline of laboratory test at V5/Wk12
6. Change from baseline of local tolerability- Application site signs/symptoms during the

study*

7. Assessment of overall application site irritation at V5/Wk12.

*Local tolerability will be evaluated on the basis of the following signs and symptoms: application site non-lesional erythema, application site exfoliation, and application site dryness, stinging, burning, itching. For each sign/symptom, a severity score will be assigned using a 4-point scale from 0 = absent to 3 = severe.

Only a sign/symptom occurring after the first application of study medication that requires additional therapy or discontinuation of treatment or judged clinically significant by the Investigator, will be documented as a TEAE.

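### The six local tolerability signs and symptoms are planned only as visit-by-visit tables, so early leavers drop out of the later per-symptom tables and signs below the TEAE threshold have no per-symptom count of patients ever affected (minor)

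*Protocol*

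**What the plan says.** The endpoint in Protocol section 6.4, item 6, is "Change from baseline of local tolerability- Application site signs/symptoms during the" study. It covers six scores, each graded 0 to 3: non-lesional erythema, exfoliation, dryness, stinging, burning and itching.

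For the analysis, section 6.6.2 states that these scores "will be listed and summarized at each visit by treatment and severity using frequency tables". The synopsis, under Safety analysis, adds descriptive statistics "at applicable time points, as well as changes from baseline by treatment arm".

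For the subjective symptoms, section 5.5.2.6 asks at site visits about the period "within the last 24 hours prior to visit".

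Section 8.3.1 lists among the reasons for mandatory discontinuation "IMP permanent discontinuation for any reason in one or both treated areas". Such patients are to have ETV procedures as far as possible. Section 5.5.1 includes in the ETV "Evaluation of local tolerability signs/symptoms" and the overall irritation grade, and Appendix A has a column for both.

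Section 6.6.2 also plans a separate table: "The overall application site irritation requested at the end of the study treatment will be listed and summarized using frequency tables by treatment group". In Table 8 of section 5.5.2.6, grade 0 of that scale is "No signs of irritation during the study" and grade 3 is for patients who stopped because of irritation.

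**The concern.** A table at V4 or V5 is conditioned on the patient still being in the trial, and remaining in the trial can depend on how well the gel is tolerated. If one arm irritates more, the affected patients are the more likely to be missing from the later rows, and the per-symptom comparison with vehicle drifts towards no difference.

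Separately, visit tables cannot be added up to a number of patients affected at any time, because they do not show whether the same patients recur.

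At stake is the symptom-level tolerability profile against vehicle. Section 5.1 lists local tolerability among the safety parameters, which it labels a primary objective, and section 3.3 argues the need for new products partly from the skin irritation seen with existing therapies. A reader of the report will want to know how many patients had stinging or dryness at all, and how severe it became.

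**Working it through.** No protocol figure has to be reproduced; the point is which summaries are planned. The passages come first, then an illustration of size.

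**Passages side by side**

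- Individual scores, sections 6.6.2 and synopsis: listings, by-visit frequency tables, and descriptive statistics with change from baseline at time points. No worst or any-time count is named.
- Early stoppers, sections 8.3.1 and 5.5.1, Appendix A: scored at an ETV that can fall at any time. No rule assigns ETV scores to V4 or V5.
- Imputation, sections 6.6.1.2 and 6.7: LOCF covers lesion counts and IGA/PGA only, so tolerability scores are not carried forward.
- TEAE rule, section 6.4: a sign or symptom becomes a TEAE only if it needs therapy, leads to stopping or is judged clinically significant. Anything milder appears only in the by-visit tables and listings.
- Overall irritation: sections 5.5.2.6 and 6.4 (item 7) tie the grade to V5; section 5.5.1 and Appendix A also collect it at the ETV; section 6.6.2 says only the end of study treatment. A patient who stopped because of irritation would not normally reach V5, so without ETV grades grade 3 would be essentially empty.

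**Visit tables and patients ever affected**

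Suppose 5% are affected at each of V3, V4 and V5 (assumed) and nobody drops out. The share ever affected is:

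- 5% if they are the same patients each time;
- 1 − 0.95³ = 14.3% if visits are independent;
- 3 × 5% = 15% if they are different patients each time.

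The three by-visit tables look the same in all three cases.

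**Effect of early stopping**

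N = 200 per arm (section 5.4.3). The rates are assumptions, since the protocol gives no expected irritation rate. Let e be the share ever affected and s the share of those who stop before Week 4 and are scored only at the ETV. Everyone else stays.

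- Patients left at each visit: N − N·e·s
- Transient (each remaining case seen at one of three visits): N·e·(1 − s)/3 affected per visit
- Persistent (each remaining case seen at all three): N·e·(1 − s) affected per visit

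| e | s | Transient, per visit | Persistent, per visit |
|---|---|---|---|
| 5% | 10% | 3/199 = 1.5% | 9/199 = 4.5% |
| 5% | 50% | 1.67/195 = 0.9% | 5/195 = 2.6% |
| 10% | 10% | 6/198 = 3.0% | 18/198 = 9.1% |
| 10% | 50% | 3.33/190 = 1.8% | 10/190 = 5.3% |
| 20% | 10% | 12/196 = 6.1% | 36/196 = 18.4% |
| 20% | 50% | 6.67/180 = 3.7% | 20/180 = 11.1% |

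Dividing the unrounded result by e, a visit table shows about 17% to 31% of the ever-affected share when irritation is transient, and 51% to 92% when it persists. With no early stopping (s = 0) the figures are e/3, or 33%, and 100%. In the transient case most of the shortfall therefore comes from the snapshots; in the persistent case all of it comes from patients leaving. In this set-up, where every case is scored at V3, V4, V5 or ETV, a worst-score table that includes the ETV recovers the full 5%, 10% or 20%.

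**The case against.** A reader might infer that patients who stop because of irritation vanish from the results, or that nothing shows how many patients were ever irritated. The protocol does not support either reading.

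- Irritation that leads to stopping must be recorded as a TEAE. TEAEs are summarised on the Safety Set by SOC, PT, severity and relationship, with special attention to local events, and the frequency of discontinuation due to TEAEs is an endpoint in its own right (section 6.4, item 2).
- The overall irritation grade looks back over the whole study, defines irritation as any sign or symptom of intolerance, and is tabulated by arm. A grade above 0 counts patients irritated at some time, though not by symptom.

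So if ten patients in one arm scored 2 or 3 and stopped before V4, the V5 symptom table could show none of them, but they would still appear as TEAEs and as discontinuations.

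Three further objections have some force. The wording of item 6 can be read as asking for the course over time, since the same words are used for vital signs. A by-visit instruction does not forbid a worst-score table, and the SAP, which is not shown here, may add one. And a worst score over a few visits is still built from 24-hour snapshots for the subjective symptoms.

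These lower the severity but do not remove the point. Section 6.6.2 does fix a by-visit analysis for these scores; it is not silent. The TEAE tables miss tolerated signs below the threshold, and one global grade cannot separate stinging from dryness. Whether ETV grades enter the overall irritation table is also not settled by the text.

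**Conclusion.** The point holds in a limited form and is minor. For the six individual signs and symptoms, the planned tables lose early leavers at later visits and give no per-symptom count of patients ever affected below the TEAE threshold. Irritation serious enough to stop treatment is reported elsewhere, so neither the overall safety conclusion nor the primary efficacy analysis depends on this.

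The size cannot be fixed from the document. The percentages above rest on assumed rates, on all irritation-related stopping falling before Week 4, and on every stopper attending an ETV. They show the direction and possible extent of understatement in a visit table, not an expected result of this trial.

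**What to change.** In section 6.6.2 (or the SAP, if it does not already do so):

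1. Keep the by-visit tables.
2. For each sign and symptom, by arm, add the number and percentage of patients by worst post-baseline severity over V3, V4, V5 and ETV, with a shift from the baseline score. The denominator is Safety Set patients with any post-baseline score.
3. Show the T2 and T10 telephone scores of the 9 to <12 age group separately. Only that group has these contacts, and section 5.5.1 has them ask about the time since the last visit as well as the last 24 hours.
4. Footnote that the subjective symptoms at site visits cover only the preceding 24 hours, so the worst score is the worst observed and can miss episodes between visits.
5. State that ETV grades enter the overall irritation table, and align sections 5.5.2.6 and 6.4 (item 7) with section 5.5.1 and Appendix A.

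All the data are already scheduled for collection. The cost is one extra table per sign or symptom, and the reported tolerability may look less favourable than the Week 12 table alone.
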